### **6.2 Inclusion/Exclusion Criterion**

#### **6.2.1 Inclusion**

- Patient  $\geq 18$  years of age
- Patient presents with ACS or stable CAD
- Patient is eligible for PCI
- Patient is willing and able to provide informed written consent
- Patient is willing to provide a DNA sample (via blood draw or saliva) for genotyping

#### **6.2.2 Exclusion**

- Patient not able to receive 12 months of dual anti-platelet therapy
- Failure of index PCI
- Patient or physician refusal to enroll in the study
- Patient with known *CYP2C19* genotype prior to randomization
- Planned revascularization of any vessel within 30 days post-index procedure and/or of the target vessel(s) within 12 months post-procedure
- Anticipated discontinuation of clopidogrel or ticagrelor within the 12 months follow up period (e.g. for elective surgery)
- Serum creatinine  $>2.5$  mg/dL within 30 days of index procedure
- Platelet count  $<80,000$  or  $>700,000$  cells/mm^3, or white blood cell count  $<3,000$  cells/mm^3 if persistent (at least 2 abnormal values) within 30 days prior to index procedure.
- History of intracranial hemorrhage
- Known hypersensitivity to clopidogrel or ticagrelor or any of its components
- Inability to take aspirin at a dosage of 100 mg or less
- Patient is participating in an investigational drug or device clinical trial that has not reached its primary endpoint
- Patient previously enrolled in this study
- Patient is pregnant, lactating, or planning to become pregnant within 12 months
- Patient has received an organ transplant or is on a waiting list for an organ transplant
- Patient is receiving or scheduled to receive chemotherapy within 30 days before or after the procedure

- Patient is receiving immunosuppressive therapy or has known immunosuppressive or autoimmune disease (e.g. human immunodeficiency virus, systemic lupus erythematosus, etc.)
- Patient is receiving chronic anticoagulation therapy (i.e. vitamin K antagonist, direct thrombin inhibitor, Factor Xa inhibitor)
- Concomitant use of simvastatin/lovastatin >40 mg qd
- Concomitant use of potent CYP3A4 inhibitors (atazanavir, clarithromycin, indinavir, itraconazole, ketoconazole, nefazodone, nelfinavir, ritonavir, saquinavir, telithromycin and voriconazole) or inducers (carbamazepine, dexamethasone, phenobarbital, phenytoin, rifampin, and rifapentine)
- Non-cardiac condition limiting life expectancy to less than one year, per physician judgment (e.g. cancer)
- Known history of severe hepatic impairment
- Patient has a history of bleeding diathesis or coagulopathy or will refuse blood transfusions
- Patient has an active pathological bleeding, such as active gastrointestinal (GI) bleeding
- Current (within 6 months) substance abuse (e.g. alcohol, cocaine, heroin, etc.)

## **7. STUDY INTERVENTIONS**

### **7.1 Intervention**

The study interventions include a blood draw, three buccal swabs (in the prospective genotype arm), a genotyping survey (first 1,000 subjects), randomization, and genotype analysis. Genotyping for *CYP2C19* will be retrospective in the conventional therapy arm and both prospective and retrospective in the *CYP2C19* prospective genotyping arm. A survey regarding patients' perceptions of genotyping and the results of genotyping will also be performed on the first 1,000 subjects.

### **7.2 Randomization**

Patients will be randomized to one of two groups. The two arms are: the conventional therapy arm in which the patients will receive clopidogrel with retrospective genotype analysis performed at the end of one year of treatment, and the prospective genotyping arm, in which patients will have prospective genotyping performed to guide anti-platelet therapy. Patients in this group who are identified to have reduced function *CYP2C19* allele will receive ticagrelor and patients with WT *CYP2C19* allele will receive clopidogrel. Drug therapy with ticagrelor and clopidogrel will be given as per clinical guidelines. Both of these drugs are FDA approved and will be given for FDA approved indications for at least 12 months after index PCI. Ticagrelor will be administered at 90 mg twice daily, and clopidogrel will be administered at 75 mg daily. All patients will receive a standard loading dose of antiplatelet therapy per the individual institution's routine clinical guidelines (prior to PCI, during PCI, or first dose after PCI), i.e. clopidogrel 300-600 mg or ticagrelor 180 mg. If patients receive ticagrelor 180 mg as a loading dose, and are then assigned to receiving clopidogrel as maintenance therapy, a loading dose of clopidogrel 300-600 mg as per institutional preference will be recommended as the next scheduled dose and 75 mg once daily as subsequent maintenance dosing. Similarly, when a transition is made from clopidogrel to ticagrelor, those loaded with 300-600 mg clopidogrel and assigned to receiving ticagrelor will get as a next scheduled dose, ticagrelor 180 mg as a loading dose and will then receive 90 mg twice daily as maintenance therapy. Specific randomization-guided treatment (i.e. clopidogrel or genotype-guided ticagrelor) will commence within 72 hours after index PCI as soon as clinically possible. If ticagrelor is discontinued

prematurely in the reduced function *CYP2C19* allele patient due to intolerance and there is no contraindication for continued dual anti-platelet therapy, the patients and their physicians will be advised to substitute ticagrelor with prasugrel at 10 mg daily (5 mg in patients weighing less than 60 kg and age  $\geq 75$  years) or clopidogrel 150 mg daily.

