Both clopidogrel and ticagrelor are FDA approved for use in patients who undergo PCI and coronary stent implantation. Ticagrelor has been shown to be superior to clopidogrel in a large trial involving 18,624 patients with acute coronary syndrome in reducing cardiovascular deaths, stroke and myocardial infarction (hazard ratio 0.84, 95% CI, 0.77-0.92). Ticagrelor has also been shown to be safer in patients undergoing coronary artery bypass graft (CABG) and has the additional benefit of reversible inhibition. However, ticagrelor caused an increased risk of non-CABG-related bleeding. In addition, prasugrel (another anti-platelet drug that irreversibly inhibits the P2Y12 receptor) has been shown to be superior to clopidogrel in reducing the risk of cardiovascular death, myocardial infarction (MI), and stroke in a large trial involving 13,608 patients with moderate-to-high-risk acute coronary syndromes with scheduled PCI (HR 0.81, 95% CI, 0.73-0.90). However, prasugrel also led to significantly higher rates of bleeding, including life-threatening and fatal bleeding. The findings from these 2 trials have been inconsistently adopted into routine use post-PCI, and the recent availability of generic clopidogrel has also contributed to the delayed uptake of prasugrel and ticagrelor into routine clinical practice of acute coronary syndrome (ACS) and post-PCI in the United States and Canada.

Routine clinical use of genotyping for *CYP2C19* in patients who undergo coronary stent implantation is not recommended due to lack of evidence as per recent guidelines published by the American College of Cardiology (ACC), American Heart Association (AHA), and Society for Cardiovascular Angiography and Interventions (SCAI). Hence, the standard of care at present is to treat all patients who undergo PCI with standard dose of clopidogrel without preemptive genotyping. If genotyping is performed and patients are preemptively identified as being predisposed to potentially inadequate platelet inhibition based on their genotype, treating these patients with a P2Y12 inhibitor (prasugrel or ticagrelor) would be a

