## **5. BASIC STUDY DESIGN**

This will be a multi-site, open label, prospective randomized trial involving ACS and stable CAD patients who come to the cardiac catheterization laboratory at Mayo Clinic, Mayo Clinic Health System (MCHS), and other U.S.A., and international sites.

Only ACS patients who come to the cardiac catheterization laboratory at the international sites, and both ACS and Non-ACS patients who come to the cardiac catheterization laboratory at Mayo Clinic, MCHS, and other U.S.A. sites will be considered for recruitment. The anticipated number of patients amongst the U.S.A. sites will be over 4,000 patients who undergo PCI per year and amongst the international sites, over 6,000 ACS patients who undergo PCI per year. Eligible, consented patients will undergo

randomization after PCI to either a conventional therapy arm or prospective genotyping arm. The conventional therapy arm patients will receive clopidogrel once daily after the index PCI and will be retrospectively genotyped for *CYP2C19*\*2, \*3 and \*17 alleles after completion of one year of treatment with clopidogrel. The prospective genotyping arm patients will be genotyped prospectively for *CYP2C19*\*2, \*3 and \*17 alleles and will receive treatment based on their genotype. In this group, patients who have the *CYP2C19* reduced function allele [i.e. \*2 allele (heterozygous or homozygous) or \*3 allele (heterozygous or homozygous)] patients will receive ticagrelor 90 mg bid. The WT *CYP2C19* patients will receive clopidogrel 75 mg once daily. If ticagrelor is discontinued prematurely in the reduced function *CYP2C19* allele patient due to intolerance and there is no contraindication for continued dual anti-platelet therapy, the patients and their physicians will be advised to substitute ticagrelor with prasugrel at 10 mg daily (5 mg in patients weighing less than 60 kg or age >75 years) or clopidogrel 150 mg daily.

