In Caucasians, the \*2 allele frequency is 15-20% and \*3 allele frequency is less than 1%, but up to 29% and 9%, respectively, in Asians. Although we are genotyping for \*3, because of its low frequency in our predominant Caucasian population, we expect to detect very few such patients in Rochester (more may be expected from the Canadian, Arizona, and Florida sites). We expect (assuming Hardy-Weinberg equilibrium) approximately 4% of patients to be homozygous for the \*2 allele (\*2/\*2), 32% to be heterozygous for the \*2 allele, and 64% to be WT. Thus, we will expect around 36% of patients that go on to PCI will be carriers of one or two \*2 alleles. However, to be conservative we will estimate 30% of the 4,255 enrolled Caucasian patients and 50% of the 1,015 Asian patients, or ~ 1,784 patients to be carriers of the *CYP2C19* reduced function allele. After randomization, we anticipate there will be approximately 892 patients in each group, i.e. the conventional therapy group receiving clopidogrel who are retrospectively identified to have *CYP2C19* reduced function allele and the prospectively genotyped group whose therapy was guided by the Spartan device results and are retrospectively identified to have *CYP2C19* reduced function.

The *CYP2C19*\*17 allele frequency in Caucasians is approximately 21-23% and 3% in Asians, and it occurs at a frequency of ~26% of Caucasian patients with the \*2 allele. The \*17 allele is considered a gain-of-function allele and has been shown in some studies to lead to enhanced response to clopidogrel (via platelet function testing) and a higher rate of bleeding events. However, other studies have not demonstrated increased platelet inhibition or altered clinical outcomes with the \*17 allele. Taken together, it is unclear how patients with the \*17 allele would respond to clopidogrel, and the combined effect of \*2 and \*17 on *CYP2C19* function and response to clopidogrel is additionally uncertain. Therefore, for the purposes of this study, \*17 will not be taken into consideration for prospective treatment decisions. However, we will utilize the \*17 information to perform retrospective secondary analyses to determine its effect (alone and in the presence of \*2 or \*3) on bleeding risk and MACE.

[figure not shown]

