In a randomized, double-blind study of patients with acute coronary syndrome, headache was reported in 6.5% of patients who received ticagrelor (n=9235) compared with 5.8% of patients who received clopidogrel (n=9186). In a randomized, double-blind study of patients with acute coronary syndrome, a greater than 50% increase in serum creatinine levels were reported in 7.4% of patients who received ticagrelor (n=9235) compared with 5.9% of patients who received clopidogrel (n=9186). Both were co-administered with aspirin and other standard therapy for 6 to 12 months. Creatinine levels generally did not progress, and often decreased with continued treatment. Dyspnea associated with ticagrelor therapy was usually mild to moderate and often resolved during continued treatment. Underlying disease should be ruled out in patients who develop new, prolonged, or worsening dyspnea during ticagrelor treatment. There is no specific treatment required if dyspnea is confirmed to be caused by ticagrelor. Ticagrelor should be continued without interruption [product information: Brilinta® oral tablets, ticagrelor oral tablets. AstraZeneca LP (per manufacturer), Wilmington, DE, 2011]. In a randomized, double-blind study of patients with acute coronary syndrome, dyspnea (exertional, nocturnal, paroxysmal nocturnal, and at rest) was reported in 13.8% of patients who received ticagrelor (n=9235) compared with 7.8% of patients who received clopidogrel (n=9186). The concomitant use of potent cytochrome P450 3A4 inhibitors (e.g. clarithromycin, ketoconazole, itraconazole, voriconazole) is associated with increased plasma levels of ticagrelor, hence patients would be at an increased risk for bleeding. Patients taking these drugs are excluded from this protocol and patients enrolled in the study will be cautioned not to commence therapy with these agents.

If ticagrelor is discontinued prematurely in the reduced function CYP2C19 allele patient due to intolerance and there is no contraindication for continued dual anti-platelet therapy, the patient and their physician will be advised to substitute ticagrelor with prasugrel at 10 mg daily (5 mg in patients weighing less than 60 kg or age $\geq$ 75 years) or clopidogrel 150 mg daily.

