In the Platelet inhibition and patient Outcomes (PLATO) trial, patients randomized to ticagrelor prior to surgical intervention for acute coronary syndrome had significantly fewer cardiovascular deaths, MI, or stroke compared with patients on clopidogrel. This analysis of PLATO, a multicenter, randomized, double-blind, double-dummy controlled trial of ticagrelor or clopidogrel in patients aged 53 to 69 years old presenting with acute coronary syndrome, compares the composite event rates in patients undergoing invasive management (coronary angiography, percutaneous coronary intervention (PCI), coronary artery bypass graft). Ticagrelor patients ( $n=6,732$ ) received a 180 milligram (mg) loading dose then 90 mg twice daily (plus placebo clopidogrel); clopidogrel patients ( $n=6,676$ ) received a 300 mg loading dose then 75 mg once daily (plus placebo ticagrelor) for 6 to 12 months. PCI patients were eligible for an additional 300 mg clopidogrel loading dose (or placebo) at investigators' discretion (event rates did not vary significantly when stratified by clopidogrel loading dose). All patients received aspirin 75 to 100 mg per day. At 12 months post-intervention, cardiovascular death, MI or stroke (primary composite endpoint) occurred in 569 (9%) ticagrelor patients compared with 665 (10.7%) clopidogrel patients [hazard ratio, 0.84; 95% confidence interval (CI), 0.75-0.94;  $p=0.0025$ ]. Incidences of cardiovascular death (5.3% vs 6.6%;  $p=0.0023$ ) and MI (3.4% vs 4.3%;  $p=0.025$ ) were significantly lower in the ticagrelor group compared with the clopidogrel group, although the incidences of stroke were not significantly different between the 2 groups. Total major bleeding [per Thrombolysis in Myocardial Infarction (TIMI) definition] occurred in 689 ticagrelor patients (11.5%) and 691 clopidogrel patients (11.6%) (95% CI 0.89 to 1.10;  $p=0.8803$ ), and severe bleeding (per Global Use of Strategies to Open Occluded Coronary Arteries definition) occurred in 185 (2.9%) of ticagrelor patients compared with 198 (3.2%) of clopidogrel patients (95% CI 0.74 to 1.12;  $p=0.3785$ ). Dyspnea occurred more frequently in ticagrelor patients compared with clopidogrel patients (13.9% versus 8%,  $p$  less than 0.0001) and was cause for discontinuing therapy in 0.8% of the ticagrelor group.

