### **15.9.3 Cross-over Monitoring**

Cross-over may potentially affect the power of the study. Patients in the conventional therapy arm who switch to ticagrelor prior to experiencing the primary endpoint may lower the event rate of the conventional therapy arm, resulting in a smaller treatment effect and lower power. Similarly, patients in the prospective genotyping arm who are assigned ticagrelor and who switch to clopidogrel may increase the event rate of the prospective genotyping arm, also resulting in a loss of statistical power. Here we define the cross-over rate as the proportion of enrolled subjects who switch from their protocol- assigned dual antiplatelet therapy to the other treatment. This does not include patients who switched to another treatment (such as prasugrel) or who stop treatment altogether, as we expect these occurrences to be rare and their effects on power difficult to predict. Each month, the cross-over rate in each arm will be calculated and the effect on statistical power according to a priori study assumptions calculated. If the revised power is less than 60%, the DSMB will be notified and asked to approve continuation of the trial. Study enrollment and activities will continue while the DSMB deliberates. The study statistician will provide power calculations for the trial based on the current cross-over rate in each arm using both a priori study assumptions as well as observed enrollment and event rates at that time. Based on the current study assumptions, a cross-over rate of 10% will, on average, result in a reduction in statistical power to around 60%.

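### Section 7.2 joins the two conditions for the reduced prasugrel dose with "and" where three other sections use "or", so read literally it doubles the advised dose in two weight/age groups

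*Combined protocol and SAP*

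**What the plan says.** The fallback for a reduced-function carrier who cannot tolerate ticagrelor appears four times in the current text. Each time the patient and physician are to be "advised to substitute ticagrelor with prasugrel at 10 mg daily" or, alternatively, to use clopidogrel 150 mg daily. Each statement cites reference 17, and each gives a lower prasugrel dose for light or older patients. The condition for that lower dose is worded differently:

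- Section 7.2 (Randomization, within Study Interventions): "5 mg in patients weighing less than 60 kg and age" at least 75.
- Section 5 (Basic Study Design): "5 mg in patients weighing less than 60 kg or age >75 years".
- Section 7.6.2 (Potential Risks, Ticagrelor): "5 mg in patients weighing less than 60 kg or age" at least 75.
- Section 11.2 (Treatment discontinuation): the same wording as section 7.6.2, with *or* and at least 75.

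No other text settles the matter. Section 7.4 on dose justification and Appendix A deal with clopidogrel and ticagrelor and give no prasugrel dosing.

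**The concern.** The trigger, default dose, alternative drug and citation are the same in all four places. They are therefore one rule stated four times, and section 7.2 is the only statement that requires both low weight and older age. A site that follows section 7.2 would advise the full dose to some patients for whom the other sections advise half of it, and every such disagreement is towards the higher dose.

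The stake is bleeding. Section 3 records that "prasugrel also led to significantly higher rates of bleeding, including life-threatening and fatal bleeding", and major or minor bleeding in carriers is the trial's secondary endpoint. The patients concerned can enroll: section 6.2 sets no weight limit and no upper age limit, and section 15.7.3 names patients aged 75 and over as a subgroup.

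**Working it through.** **The advised dose under each rule.** The plan gives no figure to reproduce here, so the check is a truth table of the literal wording (daily prasugrel dose, age in completed years):

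| Weight | Age | Section 7.2 | Section 5 | Sections 7.6.2 and 11.2 |
|---|---|---|---|---|
| under 60 kg | under 75 | **10 mg** | 5 mg | 5 mg |
| under 60 kg | 75 or over | 5 mg | 5 mg | 5 mg |
| 60 kg or more | under 75 | 10 mg | 10 mg | 10 mg |
| 60 kg or more | exactly 75 | 10 mg | 10 mg | 5 mg |
| 60 kg or more | over 75 | **10 mg** | 5 mg | 5 mg |

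In the two rows with bold entries, section 7.2 stands alone against the other three, and the ratio is 10/5 = 2. The row for age exactly 75 is a separate, smaller mismatch. It arises because section 5 uses a strict inequality, which puts it on the same side as section 7.2 for that one age.

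**How many patients this could reach.** Inputs:

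- Carriers in the genotyping arm: 892. Section 5 states that "we anticipate there will be approximately 892 patients in each group".
- Share stopping ticagrelor. The only rate in the protocol is for dyspnea, which "was cause for discontinuing therapy in 0.8% of the ticagrelor group" of an earlier ticagrelor versus clopidogrel trial (section 7.6.2, Clopidogrel). For all intolerance I assume 5–10%.
- Share of those given prasugrel rather than clopidogrel 150 mg: assumed 50–100%.
- Share falling in a weight/age group where the sections disagree: assumed 10–30%.

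Patients affected = 892 × stopping share × prasugrel share × discordant share.

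- At 0.8%: 892 × 0.008 = 7.1 stop. Low: 7.1 × 0.5 × 0.10 = 0.4. High: 7.1 × 1.0 × 0.30 = 2.1.
- At 5%: 892 × 0.05 = 44.6 stop. Low: 44.6 × 0.5 × 0.10 = 2.2.
- At 10%: 892 × 0.10 = 89.2 stop. High: 89.2 × 1.0 × 0.30 = 26.8.

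**After the correction.** With *or* in section 7.2, the two bold entries become 5 mg. The rows for under 60 kg at 75 or over (5 mg) and 60 kg or more under 75 (10 mg) do not change. At age exactly 75 and 60 kg or more, section 7.2 moves to 5 mg, and only section 5 is then left at 10 mg.

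**The case against.** The strongest reply is that the section dealing with this very event, Treatment discontinuation in 11.2, already carries *or*, as do two others. The single *and* then looks like a slip that a site would not follow over three concordant statements, and *and* can loosely be read as listing two kinds of patient. It probably is a slip. But section 7.2 sits within Study Interventions, where staff look for treatment instructions; its literal sense is that both conditions apply; and nothing tells a site which section prevails.

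Second, prasugrel is advised rather than assigned, clopidogrel 150 mg is offered equally, and the treating physician decides. Section 15.9.3 leaves switches to drugs such as prasugrel out of the cross-over rate "as we expect these occurrences to be rare and their effects on power difficult to predict". This stands, and it limits the weight of the point. It does not justify giving physicians two versions of the advice.

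Third, the documents do not show which version agrees with reference 17, and the bleeding statement in section 3 compares prasugrel with clopidogrel overall, not 10 mg with 5 mg in light or older patients. This also stands. The conflict is established from the text; the preference for *or* rests on three statements out of four and on its being the more cautious rule. Clinical confirmation should therefore precede the edit.

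Fourth, the patient counts rest mostly on assumptions. That is so: only the 892 and the 0.8% come from the protocol. The upper figure of 27 takes the top of every assumed range and should be read as a ceiling under those assumptions, not as an expectation.

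Finally, the difference between over 75 and at least 75 is minor and could have arisen when the PDF was converted. The main point does not depend on it.

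**Conclusion.** The concern holds. Section 7.2 contradicts sections 5, 7.6.2 and 11.2 on a current dosing instruction, and the direction is always towards more drug. That conclusion needs only the literal wording. The number of patients reached is small: 0.4 to 2.1 at the quoted dyspnea rate, and 2 to 27 under the assumed 5–10% stopping, both subject to the assumed prasugrel and discordant-group shares. The documents do not quantify the bleeding harm of 10 mg against 5 mg in these patients, and none is claimed here. This is an internal inconsistency that should be corrected for safety and conduct. It has no bearing on the intention-to-treat comparison, the sample size, power or type I error.

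**What to change.** 1. Have the clinical leads confirm the dose-reduction rule against reference 17.
2. If they confirm the majority wording, replace *and* with *or* in section 7.2.
3. Use a single age bound in all four places. At least 75 already stands in sections 7.2, 7.6.2 and 11.2, so only the symbol in section 5 needs to change, after a check that the source file really shows a strict inequality.
4. Send sites a short memo stating the single rule.

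The cost is one word, one symbol and a memo. Nothing in the design, sample size or analysis changes.
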